### 6.3.2 Exploratory fetal outcomes

- Reversed a-wave in the ductus venosus on fetal ultrasound
- Significant changes in heart rate patterns on the non-stress test or cardiotocograph, as defined by the attending clinician, that necessitate delivery
- Intrauterine fetal demise
- Incidence of fetal growth restriction at birth as defined by growth charts based on the local population
- Persistent reversed flow in the umbilical artery confirmed on two fetal ultrasounds
- Redistribution in the middle cerebral artery
- There is no standard classification system for the non-stress test. The attending clinician usually assess the heart rate patterns by looking at the baseline, assessing for baseline shifts, by assessing the variability, by looking at the presence or absence of accelerations and the presence of decelerations and by assessing for a sinusoidal pattern. In addition, longitudinal fetal heart rate changes are assessed. The gestational age of the fetus is also taken into consideration when assessing the non-stress test. The Royal College of Obstetricians and Gynaecologists Evidence-based Clinical Guideline Number 8 on electronic monitoring is routinely used at Tygerberg hospital for and will be used by the attending clinician to assess the cardiotocograph. ([www.nice.org.uk/nicemedia/pdf/efmguidelinerkog.pdf](http://www.nice.org.uk/nicemedia/pdf/efmguidelinerkog.pdf))

### 6.3.3 Exploratory neonatal outcomes

- APGAR score of less than 7 at 5 minutes
- Umbilical artery pH below 7.05
- Umbilical artery lactate
- Surfactant use
- Neonatal intensive care admission or special care unit admission
- Intubation and mechanical ventilation or continuous positive airway pressure (CPAP) support
- Grade III/IV hyaline membrane disease
- Length of hospital stay
- Incidence of retinopathy of prematurity

## 6.4 Biomarkers:

- Maternal plasma samples: sFlt1, sEng, endothelin 1 and metformin levels.
- Placental samples: mRNA and protein expression of HO-1, sFlt1 and endothelin 1.

(These will be addressed in a separate trial protocol)

## **Trial conduct**

### **7.1 Identification and enrolment of participants**

#### **7.1.1 Identification**

Potential participants will be identified after they have been admitted to Tygerberg Hospital (tertiary referral centre) with a diagnosis of early onset pre-eclampsia. The clinical management team will decide if the patient qualifies for expectant management and is suitable for admission as per the hospital protocol (potentially can be recruited), or delivery is likely to be imminent within 48 hours (exclusion criteria). The research midwife and principal investigator will be notified by the ward staff and/or clinical treatment team.

Normal clinical care will be maintained throughout the study. The use of steroids, antihypertensive agents and magnesium sulphate will be according to local protocols and will be decided upon by the managing clinician. The use of aspirin and calcium will be noted.

Inclusion and exclusion criteria will be assessed before approaching the patient.

#### **7.1.2 Consent**

Information about the trial will be given to the patient and a translator (working from a script) will be used if necessary. Information sheets and study details will be given to the patient and any questions about the study will be answered. A translator will be used so the patient will have the opportunity to go through the information in their own language. If they would like to be involved in the study, they will be asked to provide written informed consent. The consent form will be photocopied so that a signed copy can be given to the participant, a copy will be put in the clinical trial notes and a copy kept by the study investigators. The consent forms will be translated into English and Afrikaans. Only the study investigators and research midwives will be able to take consent. Patients will be given as much time as they need to decide whether they would like to be involved. Once the participant has signed consent she will be enrolled into the study.

#### **7.1.3 Recruitment**

Once the eligibility criteria have been checked and the informed consent document has been signed we will obtain the following:

- Baseline clinical information regarding the pregnancy (maternal age, parity, obstetric history, antenatal history, medical history, drug history, allergies, smoking status, alcohol and drug intake)
- Baseline information
  - Degree of proteinuria (24-hour protein excretion)
  - Maternal assessment (renal function, liver function, blood count)
  - Fetal assessment with ultrasound (biometry, estimated fetal weight, Doppler and amniotic fluid index findings)

## **7.2 Study treatment**

### **7.2.1 Trial drug**

After randomisation an individual treatment pack will be allocated to the participant according to an online web-based randomisation process. The participant will be allocated an individual trial number. The participant's name and trial number will be written on the pack. The packs will be identical in shape, colour, weight and feel. Each pack will contain metformin tablets or identical placebo tablets.

### **7.2.2 Packaging, formulation and supply of the treatment**

The trial drug and placebo will be produced by a contracted manufacturer. The trial drugs will be placed into containers and labelled randomly according to the computer-generated randomisation list. Labelling, storage and preparation will be done according to the requirements of the Medicines for Human Use (Clinical Trials) regulations by the trial pharmacist. Once completed the trial drugs will be collected from the pharmacy and will be stored in a locked temperature monitored cabinet. Once a participant has been randomised a unique treatment pack number will be allocated to them.

### **7.2.3 Route of administration, dosage regimen and treatment period**

Each participant will be given a treatment pack by the study nurse. A copy of the randomisation number (from the randomisation website) will be placed in the participants trial folder. The treatment pack will be labelled with the participants name and trial number. The treatment pack will contain treatment for 21 days. Treatment will then be taken twice daily until the pregnancy has ended. Trial drugs will be kept in the packaging they are provided in and will under no circumstances be used for other participants. The trial medication will be written up on the treatment chart and the chart will be signed by the nursing staff to confirm that the participant

has taken the medication and to confirm compliance. The research midwife will monitor the treatment chart to assure compliance. As a second compliance check the patient will be asked to return the empty packaging to the research midwife who will record the number of empty tablet containers at the time of delivery of the patient.

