### 4.3 Intervention

Participants will be randomised to administration of either active tablets containing metformin or an identical placebo. Once they have been recruited they will start by taking one tablet twice a day. If they have no side effects after 24 to 48 hours they will increase to 2 tablets twice a day. If again they experience no side effects after 24 to 48 hours they will increase to 3 tablets twice a day. If they are not tolerating the tablets the dose can also be decreased. The maximum dose of metformin will be 1.5mg in the morning and evening. Treatment will continue until delivery. The study will not alter or interfere with any treatment or care given routinely to women with early onset pre-eclampsia.

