### 4.4 Sample size calculations

The primary research question is does treatment with metformin result in a gain in the median length of gestation of greater than or equal to 5 days compared to the mother receiving placebo therapy. This magnitude of prolongation we believe to be a clinically important difference and likely to have important beneficial implications for the fetus (although perinatal outcomes will not be a primary outcome in this phase II study).

Given the focus on median prolongation and the skewed nature of the gestation prolongation (seen in the two trials listed below) we based sample size calculations on the Geometric Mean Ratio (GMR). Analysis was performed both using PASS 13 (Power Analysis and Sample Size Software (2014). NCSS, LLC. Kaysville, Utah, USA, [ncss.com/software/pass](http://ncss.com/software/pass)) and the Powercal program running in Stata v15 (Stata statistical software. 2017 Release 15. Stata Corp. College Station, TX: StataCorp LLC).

Power calculations settings were: 90% power, with two-sided alpha set at 0.05, control median prolongation of 8.3 days and clinically important prolongation of gestation of 5 days. The measure of variability used in this analysis is the Coefficient of Variation (CV) = (data SD)/ data Mean) in mothers treated with standard expectant management. We have two sources for gestational prolongation in pre-eclamptic mothers receiving expectant management after PE diagnosis both undertaken at the same hospital where we plan to run this trial (Tygerberg Hospital). The first was by Hall et al, who in the largest descriptive study on expectant management of early onset pre-eclampsia reported a mean gestation prolongation of 11 (SD 7) days equivalent to a CV = 0.64. The second was the PIE trial, performed by [name] et al, where patients randomized to the placebo arm had an overall mean prolongation of 13.1 (SD 12.2) days, a CV = 0.93. In this study mothers entering with greater than 29 week gestations the CV = 0.8. We have chosen to use a CV = 1.0, slightly larger than the 0.93 found in our PIE study, to allow for adequate power if greater variability in prolongation times occurs in PI2.

The results of sample size requirements for a limited range of GMR and two CVs are presented in table 1.

Table 1: Sample size calculation

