#### **7.2.4 Resupply of treatment**

It is assumed that for most patients, delivery will occur within 21 days of randomisation. However, in some cases delivery may occur after 21 days of randomisation. In these cases, continuation trial drug packs will be available. In these cases, the principal investigator will contact the randomisation office and ask for a number for a continuation pack. The continuation pack will be matched to the contents of the initial treatment pack and will contain a further 21-day supply of the treatment.

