#### **7.2.5 Dosage**

Metformin use is associated with side effects that include nausea and diarrhoea. We will start all participants on six tablets a day in divided doses. If a participant does experience side effects, we will decrease until the side effects improve. We may then increase the medication back up to 6 tablets a day if the side effects improve and the patient is willing to increase the medication again.

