17. Description of any planned adjustment for multiplicity, and if so, including how the type 1 error is to be controlled

No adjustment for multiplicity will be performed. The strategy for outcome testing is pre-specified and maintains the overall trial error rate at 0.05.

18. Confidence intervals (CI) to be reported

Standard 95% confidence intervals will be used to present analysis of the primary adjusted outcome. For secondary outcomes it is planned to the adjusted width of CI used.³

19. Adherence and Protocol Deviations

Adherence:

Trial medication will be administered to mothers on an inpatient basis. Measures to monitor adherence are: The trial medication will be written up on the treatment chart and the chart will be signed by the nursing staff to confirm that the participant has taken the medication and to confirm compliance. The research midwife will monitor the treatment chart to assure compliance. The dosing schedule details a programmed escalation of dose in the of side effects. We will use two measures of dosing in the metformin arm: (i) average daily dose of tablets = number of ingested medications/days of therapy and (ii) percentage of maximum dose = ingested medications/ total maximum medications.

Description of how adherence to the intervention will be presented:

Adherence will be presented on the two measures detailed above, using descriptive statistics (N, mean, SD, median, minimum, maximum) converted to metformin dose for the intervention arm.

Definition of protocol deviation for the trial and description in trial results:

Protocol deviations due to errors in applying inclusion/exclusion criteria, the wrong intervention being administered will be documented in trial results either in patient flow diagram or text. The primary outcome will not be subject to ascertainment error due to its unambiguous nature. Prior to unblinding of treatment all protocol deviations will be assessed, and determination made about inclusion of these participants within the trial analysis populations. Determinations will be presented in the research results in the patient flow diagram and possibly in the text.

³ Ludbrook J. Multiple inferences using confidence intervals. Clin Exp Pharmacol Physiol 2000;27:212 - 215.

19. Analysis populations.

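### Counting empty containers from a 21-day pack is too coarse to cross-check the signed chart unless the containers are small, and the SAP summarises tablets taken in the metformin arm only

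*Protocol*

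**What the plan says.** Protocol 7.2.3 sets two compliance checks for every participant. The first is the treatment chart: "the chart will be signed by the nursing staff to confirm that the participant" has taken the medication, and the research midwife monitors it. The second has the woman "return the empty packaging to the research midwife who will record the number of empty tablet containers at the time of delivery of the patient". The same section states: "The treatment pack will contain treatment for 21 days". Protocol 7.2.4 adds: "It is assumed that for most patients, delivery will occur within 21 days of randomisation". A continuation pack covers a further 21 days. Neither document schedules a count of tablets left over, and neither says how many tablets a container holds.

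The SAP's adherence section (Section D, 19) repeats the chart check and does not mention the container count. It then says: "We will use two measures of dosing in the metformin arm". These are average tablets per day and percentage of maximum dose, and both use the number of tablets ingested. SAP 24, sensitivity analysis (i), defines treatment received as an average daily dose. Draft Table 4 has rows, in both arms, for women whose tablets were decreased and women who stopped.

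The tablet schedule is described in two ways. Protocol 4.3: "Once they have been recruited they will start by taking one tablet twice a day", with steps up to three tablets twice a day. Protocol 7.2.5: "We will start all participants on six tablets a day in divided doses".

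**The concern.** A cross-check is useful only if its result changes when intake changes. If most women deliver with much of the pack unused, the number of fully emptied containers may be the same for a woman who took every tablet and for one who missed many. The check would then add little to the chart it is meant to support.

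What depends on it is limited but real: both SAP dosing measures and the treatment-received sensitivity analysis need a tablet number. The one-arm summary matters because Protocol 2.5.2.4 notes that some metformin side effects overlap with symptoms of pre-eclampsia. Placebo intake is the natural comparator for judging how much reduced intake is due to the drug and how much to the illness.

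**Working it through.** **Inputs.** Pack length 21 days (Protocol 7.2.3). Full schedule six tablets a day (Protocol 7.2.5; also the top step in 4.3). Protocol 4.4 sets "control median prolongation of 8.3 days and clinically important prolongation of gestation of 5 days"; its Table 1 uses medians of 8.32 and 13.32 days. The planning CV is 1.0, with 0.93, 0.80 and 0.64 also quoted. Assumptions: log-normal time to delivery, and one container finished before the next is opened.

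**Step 1: does the log-normal model match the plan?** On the log scale SD = √ln(1 + CV²) = √ln 2 = 0.8326. With 90% power and two-sided 0.05, n per group = 2(1.96 + 1.2816)² × 0.8326² / (ln 1.6)² = 65.9, so 66 against the stated 65. For CV 0.93 and 0.80 the same row gives 60 and 48 against 61 and 49. The model is close enough to use here.

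**Step 2: who delivers before the pack runs out?** P(T < 21) = Φ(ln(21/median)/SD).
- Placebo: ln(21/8.32)/0.8326 = 1.112, giving 86.7%.
- Metformin at the target effect: ln(21/13.32)/0.8326 = 0.547, giving 70.8%.
- Over CV 0.64 to 1.0: 87–94% and 71–78%.

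**Step 3: how full is the pack at the median?** At six a day throughout, a pack is 21 × 6 = 126 tablets.
- Placebo median: 8.32 × 6 = 49.9 used (40%), 76.1 left.
- Metformin median: 13.32 × 6 = 79.9 used (63%), 46.1 left.
- With the 4.3 step-up at 1 to 2 days per step: 43.9 to 37.9 used at 8.32 days, 73.9 to 67.9 at 13.32 days.

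**Step 4: what would the count of empties show?** Container number is an assumption, shown as a range. Entries are empty containers when 100% / 80% / 60% of six a day is taken.

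| Containers per pack | Tablets each | At 8.32 days | At 13.32 days |
|---|---|---|---|
| 1 | 126 | 0 / 0 / 0 | 0 / 0 / 0 |
| 2 | 63 | 0 / 0 / 0 | 1 / 1 / 0 |
| 3 | 42 | 1 / 0 / 0 | 1 / 1 / 1 |
| 6 | 21 | 2 / 1 / 1 | 3 / 3 / 2 |
| 21 | 6 | 8 / 6 / 4 | 13 / 10 / 7 |

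With few large containers the count carries almost no information. With many small ones it is coarse but usable.

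**Step 5: is the expected count defined?** Doses may be lowered and raised again, so no fixed number of empties is expected. The conflict over the start adds to this. If the SAP's maximum means six a day on every day of therapy (assumption), a woman who delivers at 8.32 days having taken every prescribed tablet scores 100% under 7.2.5. Under 4.3 she scores 37.9/49.9 to 43.9/49.9, or 76% to 88%.

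**The case against.** The strongest reply is that this is supervised inpatient dosing. The signed chart is the primary record in both arms, and the container count is openly a second check. Container size is not given, and the protocol speaks of containers in the plural, so the single-container case may not arise. Protocol 11.1 keeps used and unused packs to the end of the trial, so leftover tablets could still be counted. A returned-tablet count has its own blind spot: a tablet charted and then discarded looks the same as one swallowed. All of this stands. It makes the check weak rather than worthless. The plan still schedules no leftover count and does not fix a container size that would make the empties informative.

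A reader might also infer that the arms cannot be compared. The documents do not support that: chart and container data are collected from all women, and draft Table 4 sets decreased and stopped tablets side by side. Those rows count women, not tablets, so only the quantitative summary for placebo is missing. Even there, one could read the SAP as limiting only the conversion to milligrams to the active arm, but the sentence defining the two measures names that arm alone. If treatment received means metformin dose, placebo is zero and placebo tablet counts add nothing to that analysis.

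Finally, a reader might infer that a null result could not be told apart from tablets not taken. That goes too far. Besides supervised charting, metformin levels are planned in cord blood (Protocol 7.5) and listed for maternal plasma (6.4, deferred to a separate protocol). These are partial: the SAP does not use them for adherence, and a level at delivery does not give an average daily dose.

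**Conclusion.** The concern holds as a minor point about adherence measurement. Most packs will be part-used at delivery: about 87% of placebo and 71% of metformin women deliver before day 21, given log-normal times, CV 1.0 and the target effect. Unless containers are small, the count of empties is too coarse to cross-check the chart. Separately, the SAP omits this check and defines its two tablet measures for metformin only.

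The documents do not show that intake is unverifiable or that the arms cannot be compared. The effect is confined to adherence reporting and the treatment-received sensitivity analysis. The intention-to-treat estimate, its test and the sample size are untouched.

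**What to change.** In Protocol 7.2.3, replace the empty-container count with a count of tablets remaining in every dispensed container, made at delivery and whenever a continuation pack is issued. Take dispensed minus returned as the counted intake, and reconcile it with the signed chart.

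In the SAP's adherence section, name both sources, and report average daily tablets and percentage of maximum for both arms. Convert to metformin dose for the active arm only, after unblinding. State what maximum means in the denominator.

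Reconcile Protocol 4.3 with 7.2.5 on the starting tablet number, so that the expected count is defined.

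The cost is a few minutes per woman for the midwife who already collects the packaging, a field on the data sheet, and some SAP wording. Treatment, blinding and the primary analysis do not change. Reported adherence may come out lower than the chart alone would show, and discarded tablets will still go undetected.

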#### **7.2.4 Resupply of treatment**

It is assumed that for most patients, delivery will occur within 21 days of randomisation. However, in some cases delivery may occur after 21 days of randomisation. In these cases, continuation trial drug packs will be available. In these cases, the principal investigator will contact the randomisation office and ask for a number for a continuation pack. The continuation pack will be matched to the contents of the initial treatment pack and will contain a further 21-day supply of the treatment.

#### **7.2.5 Dosage**

Metformin use is associated with side effects that include nausea and diarrhoea. We will start all participants on six tablets a day in divided doses. If a participant does experience side effects, we will decrease until the side effects improve. We may then increase the medication back up to 6 tablets a day if the side effects improve and the patient is willing to increase the medication again.

### **7.3 Expectant management for pre-eclampsia**

#### **7.3.1 Routine management**

Expectant management for early onset pre-eclampsia involves admission to hospital until delivery with close maternal and fetal surveillance.

Maternal surveillance includes four hourly blood pressure measurement, twice daily clinical assessment, daily urinalysis, and twice weekly assessments with blood tests (full blood count, renal function tests and hepatocellular enzymes if HELLP syndrome is suspected) and 24-hour urinary protein measurement on admission.

Fetal surveillance includes six-hourly cardiotocography and ultrasound assessments every two weeks (or more frequently if clinically indicated) for Doppler velocimetry of the umbilical artery, middle cerebral artery, ductus venosus, amniotic fluid volume assessment and growth.

All participants will receive two doses of betamethasone 24 hours apart to reduce the risks of neonatal respiratory distress syndrome, intracranial haemorrhage and necrotising enterocolitis. A single repeat dose is usually given one week later as per hospital protocol.

Most participants will be on antihypertensive treatment and the medication used will be documented. All women should already be receiving iron and folic acid supplementation.

Clinical care will be left up to the discretion of the clinical team. The indication for delivery will be a clinical decision. Indications for delivery may include failure to control blood pressure, the development of major maternal or fetal complications. Expectant management will usually end at a gestation of 34 weeks with planned delivery.

